Title: Adjunctive Anti-Obesity Pharmacotherapy in Adolescents and Young Adults after Bariatric Surgery: A Randomized Controlled Pilot Study

NCT#: NCT04095104

Document Version Date: 07/21/2021

COMIRB Protocol

COLORADO MULTIPLE INSTITUTIONAL REVIEW BOARD [name] [contact] [contact]

Protocol #: 18-2793

Project Title: Adjunctive Anti-Obesity Pharmacotherapy in Adolescents and Young Adults after

Bariatric Surgery: A Randomized Controlled Pilot Study

Principal Investigator: [name]

Co-Investigators: [name]; [name] PhD; [name]; [name]

Version Date: 7/21/21

I. Hypotheses and Specific Aims:

Primary Aim 1: Assess the feasibility (including protocol implementation and acceptability) of a randomized, placebo-controlled, double-blinded, adjunctive 12-week phentermine + topiramate intervention beginning 6-12 months after bariatric surgery, among adolescents and young adults (age 12-24 years) who don't achieve expected weight loss or who remain severely obese (n=14 total). **Hypothesis 1**: Protocol implementation, including recruitment and retention, will be feasible based on achievement of adequate enrollment and participant completion of at least 80% of study visits. The experimental group will report better acceptability compared to the control group based on satisfaction with the desired effects of the active drugs.

Secondary Aim 2: Test the initial efficacy of standard of care plus 12 weeks of active drugs or placebo on percent weight loss beginning 6 to 12 months postoperatively.

Hypothesis 2: The experimental group will experience a greater percent weight loss than the control group at the end of the 12 week intervention period.

Secondary Aim 3: Evaluate the initial effects of standard of care plus 12 weeks of active drugs or placebo on cardiometabolic, eating behavior, and quality of life outcomes beginning 6 to 12 months postoperatively.

Hypothesis 3: The experimental group will demonstrate greater improvements than the control group in blood pressure (BP), lipids, alanine aminotransferase (ALT), hemoglobin A1c (HbA1c), and fat mass reduction; and, will report less hunger, increased satiety, more cognitive restraint, decreased daily caloric intake, increased resting metabolic rate, and better quality of life at the end of the 12 week intervention period.

II. Background and Significance:

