Phentermine as a monotherapy is FDA-approved for short-term treatment of obesity in adolescents ≥17 years. Topiramate has long been used in pediatrics for epilepsy and migraine prevention, and has been studied as an anti-obesity medication in adolescents. ²² Among the 5 medications FDA-approved for long-term treatment of obesity in adults, the combination of phentermine and extended release (ER) topiramate results in the most weight loss at 1 year in placebo-controlled clinical trials (~20lbs, 15mg/96mg dose; ~15lbs, 7.5mg/46mg dose). 23 In two large RCTs of phentermine/topiramate in adults, the odds ratio (OR) for achieving ≥10% weight loss was 11.34, and the OR for discontinuation of drug due to adverse events was 2.32 vs. placebo.²⁴ This drug combination has never been prospectively studied for obesity treatment in adolescents, despite its frequent empiric clinical use with good patient tolerance. Phentermine acts as a central nervous system stimulant through norepinephrine reuptake inhibition, resulting in appetite suppression and increased resting energy expenditure.²⁵ Topiramate's exact mechanistic effect on appetite is unclear, but is likely linked to central GABA and dopamine modulation. 25 The only RCT of topiramate for weight loss among adolescents was a pilot study in a non-surgical setting that evaluated 24 weeks at 75mg/day and found no significant difference in mean percent change in BMI, but this may have been affected by the study's 4-week run in of meal replacement.²² A retrospective review of 15mg/day phentermine + SOC vs. SOC alone among adolescents with obesity/severe obesity demonstrated a greater percent decrease in BMI at 6 months in the phentermine + SOC group vs. matched controls, with no between-group differences in blood pressure. 26 After bariatric surgery, several retrospective studies in adults have shown significant beneficial effects of anti-obesity medications (including phentermine, topiramate, and the combination) in halting weight regain and achieving additional weight loss after plateau. 27-30

Additionally, the first ever framework for the use of anti-obesity medications in adolescents

highlights the post-surgical period as one setting for which pharmacotherapy should be considered, but without a supporting evidence base.³¹ Thus, studies of anti-obesity pharmacotherapy in adolescents are needed.

III. Preliminary Studies

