- There will be a screening visit at 6, 9, or 12 months postoperatively. Eligible participants will be consented at this visit, and will be asked to come to campus ~1 week later for study visit 1. Enrollment and Visit 1 cannot be combined because it is unrealistic to screen, consent, randomize, obtain study drug, and complete additional measures after an already lengthy clinical appointment.
- The Children's Hospital Colorado Lifestyle Medicine weight management program's clinical protocols for anti-obesity pharmacotherapy require monthly clinic visits for the first three months after initiation for monitoring of effects and side effects. The proposed study protocol follows this standard.

Data Collection Tools (See Table 3. below for Schedule of Measures)

- a) Sociodemographic characteristics: age, sex, race/ethnicity, insurance, highest level of primary caregiver's education, household size and income, government-based assistance, and presence/absence of food insecurity will be obtained from the medical record and the Demographics Form.
- b) Feasibility of protocol implementation: rates of recruitment, enrollment, randomization, and dropout
- c) Study medication adherence & tolerability: assessed by 1) Questionnaire: description/dose/start date of medications, missed doses, and checklists of: effects, adverse effects, and evidence-based barriers to adherence^{51,52}; 2) Pill counts; 3) Urine amphetamine screen
- d) Self-reported changes to all non-study medications: name/dose, interim changes
- e) Patient/family satisfaction questionnaire will assess: reasons for participation, experience during study visits, satisfaction with the effect of the study medication/placebo, ease of communication with study staff, and time burden/inconvenience
- f) Biological outcome and safety measures: Weight, height, heart rate (HR), BP, basic metabolic panel, lipids, ALT, HbA1c, and pregnancy test
- g) Optional Biobanking: Gold top (serum-3.5mL blood), Purple top (EDTA-4mL whole blood), Green top (heparinized plasma-4mL blood), and Urine (volume that remains after the urine pregnancy test for females and a separate urine collection for males) will be collected with participant assent/consent for future research questions.
- h) 3-day dietary record: Participants will complete a dietary record on 3 consecutive days (2 weekday, 1 weekend day) based on standardized protocols for dietary assessment.⁵³

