Route of Data Collection: To reduce in-person time on campus for participants, components of Study Visits 1-4 will be collected remotely (designated by superscript "R" in Table 3 below) either via secure video call or telephone call (with questionnaires emailed) in the participant's/guardian's preferred language within the same week and ideally on the same day as the study visit. These measures will be conducted remotely unless it is not possible or places an undue burden on the participant to do so (e.g. participant does not have a reliable internet connection or has a limited phone data plan that incurs significant charges). Pill count will require a video connection. All other measures require in-person collection/administration to appropriately collect outcome/safety data.

Table 3. Schedule of Measures

"X"= Study specific "O"= Standard of Care #= Bariatric Clinic or CHCO CTRC ‡= + Adult CTRC or CHCO Radiology/CTRC R= can be delivered remotely	SCREENING/ ENROLLMENT# 6-12 mo post- op	STUDY VISIT 1#,‡ ~1wk after Enrollment	STUDY VISIT 2# 4wks after Visit 1	STUDY VISIT 3# 4 wks after Visit 2	STUDY VISIT 4#,‡ 4 wks after Visit 3
Review of Inclusion/Exclusion criteria	Х				
Echocardiogram (ONLY for those with Hypertension or Severe OSA with poor PAP adherence IF not obtained in the prior 6 months)	0				
Demographics Form		X ^R			
Feasibility of protocol implementation (e.g. enrollment rates, dropout rates)	х	х	X	х	X
Study medication adherence & tolerability- Study Med Form			X ^R	X ^R	X ^R
Study medication adherence- (pill count)- Study Med Form			X ^R	X ^R	X ^R
Study medication adherence (urine amphetamine screen)		X	X	X	X
Review of all non-study medications (self-report)	Х	X ^R	X ^R	XR	X ^R
Patient/family satisfaction survey					X ^R
Weight, Height, Temperature, HR, BP; Review of Systems; Physical exam		X	Х	X	X
Urine pregnancy test	X	X	X	X	X
Lipid panel, ALT, HbA1c	Х				Х
Basic metabolic panel	Х		Х		X
Optional Biobanking	Х		Х		X
3-day diet record review		X ^R			X ^R
Previous Day Physical Activity Recall (PDPAR)		X ^R			X ^R

IWQOL-Kids (≤19yo)/-Lite (≥ 20yo) & Parent Report		X ^R			X ^R
PedsQL (general health-related quality of life)		X ^R			X ^R
CES-D (Depression Screen)	0	X	X	Χ	X
C-SSRS (Suicide Screen)	X	X	X	Х	X
Resting metabolic rate		X			X
DEXA-3 site		X			Х
Clinical Intervention/Translation Core: Eating behavior questionnaires (VAS, TFEQ, EAH)		X ^R	X ^R	X ^R	X ^R

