Sample size justification: Based on recommended practice for pilot studies, 60 the minimum sample size (10 total participants, 5 per arm) is driven by the primary aim of the study and represents a balance between participant availability (patient volume and recruitment timeline), and acceptable precision around feasibility estimates (Aim 1), which will be used for subsequent study planning. It is not based on a power calculation for group differences seen in any Aim 2 or 3 measures. To estimate precision around dropout and medication tolerability rates, we used a confidence interval approach with normal approximation of the binomial calculation 60-62. First, we estimate that a realistic dropout rate is 25%, based on 3 prior anti-obesity medication RCTs conducted in obese adolescents. 22,63,64 A realistic medication tolerability rate (% who do not discontinue medication because of adverse effects) is 85%, based on the single RCT of topiramate in adolescents and two larger RCTs of phentermine/topiramate XR in adults. ^{22,65,66} Dropout: With the minimum of 10 adolescent/young adult participants, if our observed dropout rate is 25%, we can be 68% confident that the enrollment rate estimate is accurate within 13 percentage points (or 90% confident that it is accurate within 20%). With 14 adolescent/young adult participants, if our observed dropout rate is 25%, we can be 68% confident that the enrollment rate estimate is accurate within 11 percentage points (or 90% confident that it is accurate within 18%). Medication tolerability: With 10 adolescent/voung adult participants, if our observed medication tolerability rate is 85%, we can be 68% confident that the tolerability estimate is accurate within 9 percentage points (or 90% confident that it is accurate within 16%). With 14 adolescent/young adult participants, if our observed medication tolerability rate is 85%, we can be 68% confident that the tolerability estimate is accurate within 9 percentage points (or 90% confident that it is accurate within 15%). Given possible constraints around enrollment, the level of precision with 10 or 14 adolescents/young adults was deemed acceptable to achieve protocol refinement for future RCT development.

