Planned analyses: Descriptive statistics will characterize the study population. Independent samples t-tests will be performed for continuous variables and chi-square for categorical variables to determine statistically significant differences between experimental and control groups. Aim 1: Feasibility of acceptability (adherence, tolerability, and satisfaction) will be descriptively assessed using differences in proportions between experimental and control groups. Feasibility of protocol implementation will be established by determining the proportions (rates) of recruitment, enrollment, randomization, and dropout. Aims 2,3: Estimated means and variability of continuous health outcome variables (e.g. % change in weight) and intra- and intersubject variability of repeated measures (e.g. loss of control eating) will be graphically presented and visually compared for experimental vs. control groups, as this aim is not powered to run inferential statistics.

G. Summarize Knowledge to be Gained:

The goal of this study is to establish the feasibility and initial efficacy of two common anti-obesity medications for adolescents who require additional risk reduction following bariatric surgery.

Adolescents with severe obesity who don't achieve optimal weight loss and co-morbidity improvement after bariatric surgery have few evidence-based treatment options to mitigate significant health risks through the remainder of adulthood. This study has the potential for substantial impact regardless of results, given that anti-obesity medications are currently being used in the post bariatric surgery setting without an evidence base. A recent international pediatric obesity webinar (4/2019) with contributors from leading adolescent bariatric surgery centers strongly expressed need and enthusiasm for studying the role of pharmacotherapy after surgery. Our center's volume, interdisciplinary expertise, and existing IND to study these medications in this setting sets us apart as the best positioned adolescent bariatric surgery center to carry out this initial pilot, with high potential for a subsequent larger multi-site RCT to evaluate safety and efficacy, mechanism of action, and predictors of response.

H. References:

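### The satisfaction survey behind Hypothesis 1 is given only at Visit 4, so participants who leave the study contribute no satisfaction data and the arm comparison can be biased in either direction

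*Combined protocol and SAP*

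**What the plan says.** Section I, Hypothesis 1, makes one between-arm prediction about acceptability: "The experimental group will report better acceptability compared to the control group based on satisfaction with the desired effects of the active drugs".

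Section IV.D, Data Collection Tools, item (e), describes the questionnaire that measures this. It covers, among other things, "satisfaction with the effect of the study medication/placebo", visit experience and time burden. In Table 3 the row "Patient/family satisfaction survey" has a single mark, under Study Visit 4, flagged as deliverable remotely. By contrast, the row "Study medication adherence & tolerability- Study Med Form" is marked at Visits 2, 3 and 4.

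Section IV.F, Planned analyses, Aim 1, names adherence, tolerability and satisfaction as the parts of acceptability and says they "will be descriptively assessed using differences in proportions between experimental and control groups". It states no denominator and no handling of missing responses. Section IV.A lists only adherence and tolerability under acceptability, so satisfaction enters through Hypothesis 1 and Section IV.F.

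On attrition, the sample size justification in Section IV.F takes 25% as a realistic dropout rate. It treats this separately from the 85% expected not to stop medication for adverse effects. Item 6(d) of the Data and Safety Monitoring Plan keeps participants who stop one or both drugs on the visit schedule if they consent. Table 3 has no early-withdrawal column, and none of the eight standard phone calls listed after it is assigned the satisfaction survey.

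**The concern.** A participant who leaves before Visit 4 can already have given adherence and tolerability data at Visits 2 and 3, but gives no satisfaction data at all. Leaving may itself reflect low satisfaction with the drug effect or with the burden of the study. Section IV.E names time demands as a reason families may not complete. If so, the people who answer the survey are a favourable selection, and the between-arm difference depends on who left each arm.

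What is at stake is a misleading descriptive estimate. With at most 7 per arm, one or two missing answers move the proportions by many points, and the plan does not ask for the number of responders to be shown beside them. The pilot also loses feedback from the participants whose views would matter most for refining a later trial.

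**Working it through.** **Inputs from the plan.** 14 participants, 7 per arm (Section IV.B); minimum 10, 5 per arm, and 25% dropout (Section IV.F).

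**The plan's own figure.** Section IV.F gives precision for dropout and for tolerability, and none for satisfaction. For dropout with n = 14 it states 11 points (68% confidence) and 18 points (90%). The half-width is z × √(p(1−p)/n). With the whole count 3/14 (p = 0.214) this gives 10.9 and 18.0, which reproduces the statement. At exactly p = 0.25 it gives 11.5 and 19.0. These figures describe the dropout rate and say nothing about the satisfaction comparison.

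**Expected missing surveys.** 0.25 × 14 = 3.5, leaving 10.5 able to answer. At the minimum size, 0.25 × 10 = 2.5, leaving 7.5.

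**Illustration.** The documents give no satisfaction rate, so this part is assumed: s = 4 of n = 7 are truly satisfied in each arm (57.1%), the true difference is 0, and only dissatisfied participants leave. If d leave an arm, the observed proportion is s/(n − d).

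| Dissatisfied dropouts, active vs placebo | Observed, active | Observed, placebo | Spurious difference |
|---|---|---|---|
| 2 vs 2 | 4/5 = 80.0% | 4/5 = 80.0% | 0 points |
| 2 vs 1 | 4/5 = 80.0% | 4/6 = 66.7% | +13.3 points |
| 3 vs 1 | 4/4 = 100% | 4/6 = 66.7% | +33.3 points |
| 1 vs 2 | 4/6 = 66.7% | 4/5 = 80.0% | −13.3 points |
| 1 vs 3 | 4/6 = 66.7% | 4/4 = 100% | −33.3 points |

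If assumed true satisfaction varies from 3/7 to 6/7, an imbalance of one dissatisfied dropout moves the difference by about 7 points (3/6 − 3/7 = 50.0% − 42.9%) to 17 points (5/5 − 5/6 = 100% − 83.3%).

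**The mix matters as well as the count.** If one arm loses 2 dissatisfied and 2 satisfied participants, it shows 2/3. If the other loses 1 dissatisfied participant, it shows 4/6. Both are 66.7%, so there is no spurious difference despite unequal dropout.

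**How likely is the 3 versus 1 split?** Its dropout odds ratio is (3/4)/(1/6) = 4.5, and 4 of 14 is 29% dropout. For scale only, suppose dropout is 25% overall with an odds ratio of 2.32 between arms. That gives about 33% versus 17%, or 2.3 versus 1.2 of 7. If every dropout is dissatisfied, the survey shows 4/(7 − 2.3) = 85% versus 4/(7 − 1.2) = 69%, a 16-point difference.

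**Effect of the proposed reporting.** If every withdrawer answers at exit, the denominators return to 7 and 7 and the spurious difference is 0. If none answers, the bounds for an arm with m non-responders are s/7 and (s + m)/7. For the 3 versus 1 case, active runs from 4/7 to 7/7 and placebo from 4/7 to 5/7. The difference then lies between 4/7 − 5/7 = −14 points and 7/7 − 4/7 = +43 points. That range contains the true value of 0, which the bare 33-point figure hides.

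**The case against.** The strongest case against making much of this has five parts.

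- **Scope.** A reader might infer that the whole acceptability comparison is confined to completers. The documents do not support that. The Study Med Form is collected at Visits 2, 3 and 4, adverse-effect calls are made in weeks 1 to 3, and dropout is itself a reported Aim 1 outcome. Only satisfaction hangs on Visit 4. This stands.
- **Direction.** A reader might also infer bias in favour of active drug from the Background statement that "the OR for discontinuation of drug due to adverse events was 2.32 vs. placebo". That figure comes from adult trials and concerns stopping drug, not leaving the study. Here, participants who stop drug and consent stay on schedule and can reach the survey. The hypothesis concerns "satisfaction with the desired effects of the active drugs", so placebo participants disappointed by lack of effect could equally be the ones to leave. The direction is open. This stands.
- **Certainty and size.** The bias is zero if dropout is unrelated to satisfaction or if both arms lose the same mix. The 33-point case is an extreme split. This stands, and is why a range including zero and the reversed sign is given.
- **Timing.** Visit 4 is a sensible time to rate a 12-week intervention. An exit survey rates a shorter exposure, possibly before goal dose, and someone lost before Visit 1 has no drug effect to rate. Counting every non-responder as dissatisfied would misclassify people who left for travel or time. These points shape the fix but do not remove the gap.
- **Consequence.** The comparison is descriptive and has no threshold. Hypothesis 1's numerical benchmark concerns visit completion. This limits the importance of the point, but the satisfaction prediction is still part of the primary aim, and the plan as written yields satisfaction data only from those who reach Visit 4.

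**Conclusion.** The point holds for the satisfaction component of acceptability. As scheduled, participants who leave the study, about 3 to 4 of 14 at the plan's own dropout rate, supply no satisfaction data, and the analysis does not say what denominator is used. The count is approximate because the plan does not define dropout as occurring after randomisation.

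The resulting bias is a conditional risk. It requires dropout to be related to satisfaction and the mix lost to differ by arm. Under the assumed 4/7 satisfaction with only dissatisfied dropouts, it is 0, 13 or 33 points for the three splits shown, with either sign. Because the comparison is descriptive, the harm is a misleading estimate and lost feedback, not a false-positive test. The change is worth making because it is cheap and the missing answers may well be informative.

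**What to change.** 1. In Table 3, footnote the satisfaction survey and the Study Med Form: administer remotely at Visit 4, or at withdrawal from the study after study drug has started, whichever comes first, and record the time on drug at completion. Both rows are already marked for remote delivery.
2. In Section IV.F, Planned analyses, Aim 1, add that satisfaction will be reported by arm with the number randomised and the number responding. Give the responder proportion alongside best- and worst-case bounds over all randomised participants (non-responders all satisfied, then all not satisfied). Show the matching range for the between-arm difference. The worst case is a bound and should not be presented as the estimate.

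The cost is one footnote, one or two analysis sentences and roughly 3 to 4 short questionnaires. Some withdrawers will not reply, ratings will come from differing lengths of exposure, the bounds will be wide with 7 per arm, and the satisfaction figure may be less favourable. No treatment or clinical rule changes.
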